#### 1.1.9.5 Positive predictive value (PPV) on a per-patient and per-region basis Analysis:

PPVs on a per-patient and per-region-basis of F-DCFPyL PET for detection of tumor location confirmed by histopathology/biopsy, clinical and conventional imaging follow-up will be calculated and reported along with the corresponding two-sided 95% confidence intervals. The confidence intervals will be constructed using the Wilson score method. PPV will be reported for each of the three blinded readers independently.

Detection rates on a per-patient basis of  $^{18}$ F-DCFPyL PET stratified by PSA value (0.2 - <0.5, 0.5 - <1.0, 1.0 - <2.0, 2.0 - <5.0,  $\geq$ 5.0) will be summarized in tabular format and compared between PSA strata using chi-square analysis.

Detection rate is defined as number of patients with F-DCFPyL positive disease, independent of pathology, imaging or clinical follow-up. A detection rate will be reported for each reader independently stratified by PSA.

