# **Secondary Endpoints:**

- 1. Prognostic value of the F-DCFPyL PET/CT miTNM classification (described below) for biochemical PFS, radiographic PFS and overall survival.
- 2. Positive predictive value (PPV) on a per-patient and per-region basis (Table 1) of F-DCFPyL PET for detection of tumor location confirmed by histopathology/biopsy or follow-up assessed separately for initial staging and restaging.

Region	Description
1	Prostate Bed
2	Pelvic lymph nodes
3	Extrapelvic soft tissue, lymph nodes and visceral metastases
4	Bone metastases

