#### False positive

- For patients undergoing systemic treatment (alone or in combination with targeted treatment): If on post-treatment follow-up imaging within 3-12 months, lesions seen on CT or MRI increase by more than 20% in long axis diameter and PSA decreases by more than 50%.
- 2) In subjects with localized suspected lesions(s) receiving targeted treatment without concomitant systemic treatment there are two ways to meet false positive disease:
  - If the subject does not demonstrate a decrease of PSA by greater than 50% after targeted treatment [OR]
  - If on post-treatment follow-up imaging within 3-12 months, lesions seen on CT or MRI increase by more than 20% in long axis diameter (with a minimum of 3 mm in change in size).
- 3) For untreated patients: If on follow-up imaging within 3-12 months, lesions seen on CT or MRI decrease by more than 30% in long axis diameter (with a minimum of 3 mm in change in size).

If all regions in a patient/region do not meet criteria for either True positive or False positive disease, then the patient/region will be considered unevaluable for primary endpoint.

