#### True positive:

- 1) If there was a corresponding positive sclerotic lesion on the CT portion of the  $^{68}$ Ga- $^{18}$ F-DCFPyL PET or on a separate CT obtained  $\leq$  30 days before or after the PET/CT in the same location as the PSMA uptake.
- 2) If there is focal uptake seen in the same location as the PSMA uptake on the baseline bone scan performed within one month of F-DCFPyL PET.
- 3) If there is a lesion noted in the same location as the PSMA uptake on the initial MRI performed within one month of F-DCFPyL.

- 4) If within 12 months follow-up CT demonstrates development of sclerosis in the same location as the PSMA uptake.
- 5) If within 12 months follow-up MRI demonstrates a new bone lesion in the same location as the PSMA uptake.
- 6) If within 12 months follow-up bone scan demonstrates new focal uptake in the same location as the PSMA uptake.
- 7) In subjects with localized suspected bone lesion(s) receiving targeted treatment without concomitant systemic treatment:
  - If the subject demonstrates a decrease of PSA by greater than 50% after targeted treatment.

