#### 1) Patient level evaluation:

- a) *True positive patient*: A single region in a patient contains a true positive node either by pathology or imaging/clinical follow-up.
  - i) For a patient to be considered a True Positive, only one region is required to have a true positive lesion as described above, unless one region is categorized as a false positive based on pathology. This means that a single pathology false positive region outweighs regions with imaging/clinical follow-up true positive disease.
  - ii) A patient will be considered a True Positive if one region contains a lesion that is True Positive, even if other regions are categorized as inevaluable or false positive based on imaging or clinical follow-up.

- b) *True negative patient*: in the absence of True Positive or False Positive lesions, a patient will be considered a True Negative if there is pathology that is negative for disease and corresponding lesion is negative by F-DCFPyL PET.
- c) False positive patient:
  - i) Pathology confirms a false positive lesion that is read as positive on F-DCFPyL PET.
  - ii) In the absence of pathology: there are no true positive regions, and there is a region that is categorized as false positive based on imaging or clinical follow-up.
- d) False negative patient: in the absence of True Positive or False Positive lesions, a patient will be considered a False Negative if there is pathology that is positive for disease and corresponding lesion is negative by F-DCFPyL PET.
- 2) Region level evaluation: Each patient will have four evaluable regions (Table 1: prostate bed, pelvis, extrapelvic soft tissue, and bone metastases). Each region will be categorized as true positive or false positive as described above. Regions without evidence of F-DCFPyL positive disease or deemed unevaluable will not be included in the analysis.
  - a) True positive region:
    - i) Pathology confirms a F-DCFPyL avid lesion as a true positive in the region. ii) In the absence of pathology, clinical or imaging follow-up demonstrates a true positive lesion within the region independent of the presence of an inevaluable lesion or a false positive lesion (ie true positive disease will supersede a false positive lesion in the region based analysis if based on imaging/clinical follow-up).

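### If per-region PPV is pooled over the four regions, the planned Wilson interval ignores within-patient correlation and is too narrow; the plan should say whether it pools, and cluster by man if it does

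*Combined protocol and SAP*

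**What the plan says.** The second secondary endpoint (section 1.1.3.3) is "Positive predictive value (PPV) on a per-patient and per-region basis (Table 1) of" the PET scan, assessed separately for initial staging and restaging. Section 1.1.9.5 says both versions will be "reported along with the corresponding two-sided 95% confidence intervals", and names one method for them: "The confidence intervals will be constructed using the Wilson score method". PPV is reported separately for each of three blinded readers.

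The region-level definitions in section 1.1.8.4, part C, say "Each patient will have four evaluable regions" and class each as true or false positive. Regions that are PET-negative "or deemed unevaluable will not be included in the analysis". A scan therefore contributes between zero and four regions.

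The verdicts come from pathology or from the follow-up rules in section 1.1.8.4, part A. For lesions given targeted treatment without systemic treatment, one true-positive route is "If the subject demonstrates a decrease of PSA by greater than 50% after targeted treatment" and one false-positive route is "If the subject does not demonstrate a decrease of PSA by greater than 50% after targeted treatment".

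Sections 1.1.3 and 1.1.4 allow re-enrolment for a later management decision, and section 1.1.9.2 analyses the whole cohort as well as the initial and subsequent groups. No section mentions clustering, robust variance, resampling by patient, or repeat scans of the same man.

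**The concern.** The Wilson interval takes its width from the number of independent binary observations. Regions within one patient share a PSA course and a treatment, and the protocol's own reference standard uses both. If such regions are counted as separate observations, the information in the sample is overstated.

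The interval is the only measure of precision planned for this endpoint, so an interval that is too short would make the per-region PPV look more certain than it is. Re-enrolment adds a second source of dependence, because one man may contribute several scans to the whole-cohort or restaging results. That source is present even if each region type is reported alone.

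**Working it through.** **1. Does the reference standard link regions?** The follow-up rules in section 1.1.8.4, part A, compare as follows.

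- *Targeted treatment only.* A PSA fall above 50% is enough for true positive in visceral, bone and prostate lesions, and in nodes that do not enlarge. Absence of that fall is enough for false positive in nodes, visceral and prostate lesions, and in bone after curative-intent treatment. One PSA result can thus label several regions.
- *Systemic treatment.* PSA change enters the nodal and visceral rules in both directions, and the prostate false-positive rule. The prostate true-positive rule uses size only.
- *Untreated.* The nodal, visceral and prostate rules use size only.
- *Bone.* Six of the seven true-positive routes use imaging at the lesion's own site.

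Positive correlation is therefore the expected case, but the rules do not fix its size.

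**2. Inputs.** From the plan: Wilson score, two-sided 95%, at most four regions per scan. The plan gives no expected PPV, number of positive regions, ICC or target precision for PPV, so there is no planned figure to reproduce. Assumed: 100 evaluable PET-positive patients, PPV 0.8 or 0.9, ICC 0.1 to 0.5, and two distributions of 1, 2, 3 or 4 positive regions:

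- Mix A, 65/20/10/5%: mean m = 0.65 + 0.40 + 0.30 + 0.20 = 1.55; mean m² = 0.65 + 0.80 + 0.90 + 0.80 = 3.15.
- Mix B, 40/30/20/10%: mean m = 0.4 + 0.6 + 0.6 + 0.4 = 2.0; mean m² = 0.4 + 1.2 + 1.8 + 1.6 = 5.0.

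**3. Design effect.** With unequal cluster sizes, DEFF = 1 + (mean m² / mean m − 1) × ICC. The ratio is 3.15/1.55 = 2.03 for A and 5.0/2.0 = 2.50 for B. The interval widens by about √DEFF. Coverage of plain Wilson is from a beta-binomial simulation (4,000 runs per setting).

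| Mix | ICC | DEFF | √DEFF | Coverage of plain Wilson |
|---|---|---|---|---|
| A | 0.1 | 1.10 | 1.05 | 93–94% |
| A | 0.3 | 1.31 | 1.14 | 91–92% |
| A | 0.5 | 1.52 | 1.23 | 89–90% |
| B | 0.1 | 1.15 | 1.07 | 93–94% |
| B | 0.3 | 1.45 | 1.20 | 89–90% |
| B | 0.5 | 1.75 | 1.32 | 86–87% |

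A mix with fewer patients at three or four regions is milder. With 62/28/8/2%, mean m is 1.50 and mean m² is 2.78; at ICC 0.1, DEFF = 1 + (1.853 − 1) × 0.1 = 1.085 and √DEFF = 1.04. Over such mixes the range is about 4–32% wider, with coverage of about 86–95%.

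**4. In percentage points.** The Wilson limits are [p + z²/2n ± z√(p(1−p)/n + z²/4n²)] / (1 + z²/n), with z = 1.96. The adjusted interval uses n/DEFF.

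- Mix A, n = 155, p = 0.9: plain 84.3–93.8%. ICC 0.1 (n/DEFF = 140.5): 83.9–93.9%. ICC 0.5 (102.2): 82.7–94.4%.
- Mix B, n = 200, p = 0.8: plain 73.9–85.0%. ICC 0.5 (200/1.75 = 114.3): 71.7–86.3%.

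**5. Controls.** At ICC 0 the simulated coverage of plain Wilson is about 95%, so the shortfall comes from clustering and not from the Wilson formula. Wilson with a patient-level robust variance returned 94–95% in every setting of the table. Doubling to 200 patients left plain-Wilson coverage almost unchanged, so a larger sample does not cure the problem.

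**The case against.** The strongest reply is that pooling is nowhere stated. The endpoint definition points to Table 1, which names four regions, so four region-specific PPVs are a natural reading. Each scan would then add at most one observation to any interval, and plain Wilson would be sound apart from re-enrolled men. This stands, and it makes the point conditional. A reader might infer that the plan does pool and that its interval will certainly miss 95% coverage. The documents do not go that far: the region-level section says how regions are classified and excluded, which suggests a single analysis, but it does not say that they are combined.

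A reader might also take the shared image reader as a cause of correlation. It is not one here, because PPV is reported per reader and every region in an interval has the same reader.

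Nor are all verdicts tied by construction. Many rules rest on lesion size or local imaging, and pathology takes precedence where it exists. Under systemic treatment, the main nodal and visceral rules ask for the same PSA fall on both sides, so among men with that fall lesion size decides. The correlation could be small; at ICC 0.1 the loss of coverage is only one or two points.

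Finally, this is a secondary endpoint with no test, threshold or sample size attached. That limits the consequence but does not make an overstated precision correct.

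**Conclusion.** The point holds in conditional form. If per-region PPV is pooled and within-patient correlation is positive, the planned 95% interval is too narrow. The first condition is suggested by the text but not stated; the second is likely from the PSA and treatment rules. The size, about 4–32% in width and coverage of about 86–95%, rests wholly on the assumed ICC, PPV and region counts. In the examples above, the limits move by between 0.1 and 2.2 percentage points.

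The point estimate and the primary endpoint are unaffected. Per-patient and single-region-type intervals are affected only through re-enrolled men. The plan's silence on pooling and on repeat scans should be resolved whichever reading was intended.

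**What to change.** Add to section 1.1.9.5:

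1. A statement of whether per-region PPV is pooled over regions, given for each region type, or both.
2. For any pooled PPV, a patient-clustered interval in place of plain Wilson. Any of three will do: Wilson on the effective sample size (n/DEFF, with DEFF from a patient-level robust variance), GEE with robust variance, or a bootstrap that resamples patients. All scans of a re-enrolled man form one cluster.
3. Plain Wilson for per-patient and single-region-type PPV only where each man contributes one scan to that interval; otherwise cluster by man there too.
4. A fallback for the case where every region in the interval is a true positive. The robust variance is then zero, and a bootstrap gives no width. Wilson with the number of men as n is a simple conservative choice.

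The cost is a few sentences, a few lines of code and a slightly wider interval. Data collection and study conduct do not change.

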# 1.1.4 INCLUSION EXCLUSION CRITERIA

#### Inclusion criteria

- 1. Patients who fulfill criteria for initial staging or restaging as outlined below:
- 1) Initial treatment strategy decisions (initial staging)

All patients with histologically proven prostate cancer or strong suspicion of prostate adenocarcinoma based on very high PSA levels (>50 ng/mL) who require an initial treatment/management decision who may be candidate for any of the following strategies:

- A) Surgery
- B) External radiation therapy (RT) C) Other focal therapies
- D) Systemic medical treatment E)

Watchful waiting

- 2) Assessment for Subsequent treatment strategy (restaging), any of the following:
  - A) Patients with biochemical recurrence who are potential candidates for any salvage treatment. Biochemical recurrence is defined by rising PSA after definitive therapy with prostatectomy or radiation therapy, as any of the following:
    - a. Post radical prostatectomy (RP): PSA equals to or greater than 0.2 ng/mL measured more than 6 weeks after RP
    - b. Post-radiation therapy: Nadir + greater than or equal to 2 ng/mL rise in PSA
  - B) Patients with known prostate cancer who undergo restaging because of new symptoms
  - C) Patients with known metastatic prostate cancer who undergo restaging because of rising PSA with negative or inconclusive conventional imaging
  - D) Patients with known prostate cancer who are treated medically or with RLT in whom response to treatment is assessed
- 2. Capability to provide written informed consent
- 3. Able to remain still for duration of each imaging procedure (about 30 minutes)
  - \* Patients may be reenrolled in the study, if F-DCFPyL PET/CT is performed for subsequent management decision.

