# 1.1.9.2 Analysis Population

Endpoints will be analyzed for the entire patient cohort and for treatment groups separately (Initial and subsequent).

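### The planned comparison of detection rate across PSA strata ignores entry route, although the eligibility rules give the routes different PSA floors, so a difference between strata can partly reflect case mix.

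*Combined protocol and SAP*

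**What the plan says.** Section 1.1.9.5 reports the per-patient detection rate "stratified by PSA value (0.2 - <0.5, 0.5 - <1.0, 1.0 - <2.0, 2.0 - <5.0", with a fifth stratum of 5.0 or more. The rates "will be summarized in tabular format and compared between PSA strata using chi-square analysis", and a rate is reported for each reader. A patient counts as detected if the scan shows positive disease, "independent of pathology, imaging or clinical follow-up". No covariate, second stratification factor or restriction of the population is given.

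The inclusion criteria (section 1.1.4) admit patients by several routes:

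- Recurrence after prostatectomy (2A a): "PSA equals to or greater than 0.2 ng/mL measured more than 6 weeks after RP".
- Recurrence after radiation (2A b): "Post-radiation therapy: Nadir + greater than or equal to 2 ng/mL rise in PSA".
- Initial staging: histologically proven cancer with no PSA limit, or "strong suspicion of prostate adenocarcinoma based on very high PSA levels (>50 ng/mL").
- Other restaging (2B to 2D), with no minimum PSA: for example, 2B is "Patients with known prostate cancer who undergo restaging because of new symptoms". Route 2C is known metastatic disease with rising PSA, and 2D is response assessment on treatment.

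Section 1.1.9.2 adds: "Endpoints will be analyzed for the entire patient cohort and for treatment groups separately (Initial and subsequent"). It does not divide the subsequent group by recurrence type.

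**The concern.** A cross-stratum test of detection will usually be read as showing how detection depends on PSA. That reading needs the kind of patient to be similar across strata, or the analysis to allow for the difference. Here part of the difference is built into eligibility. Two routes cannot contribute to the lower strata at all, while recurrence after prostatectomy can contribute to all five.

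The type of patient can plausibly affect whether a scan is positive. Detection needs no confirmation, so uptake in a prostate still in place is enough. The protocol's own staging framework (section 1.1.8.2, local tumor) separates disease with the prostate in place, treated or not, from local recurrence after prostatectomy.

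What is at stake is the interpretation of one table and its test. A referring physician wants to know how likely a positive scan is at a given PSA for a given type of recurrence, and the pooled table does not answer that.

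**Working it through.** The documents give no expected detection rate, sample size or power for this comparison, so there is no stated figure to reproduce. The check has two parts.

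**1. Which strata each route can reach.** This takes the PSA used for stratification to be the qualifying PSA. A nadir cannot be negative, so nadir + 2 or more means PSA of at least 2.0.

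| Entry route | PSA floor (ng/mL) | Reachable strata |
|---|---|---|
| 2A a, after prostatectomy | 0.2 | all five |
| 2A b, after radiation (qualifying only by this rule) | 2.0 | 2.0 to <5.0 and 5.0 or more |
| Initial staging without histology | above 50 | 5.0 or more only |
| Initial staging with histology | none | all five |
| 2B, 2C, 2D | none | all five |

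Among biochemical recurrences, the three strata below 2.0 can hold only patients who meet the post-prostatectomy rule. The top two can hold both kinds. This follows from the text alone.

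**2. How much this could matter.** Group shares and group-specific rates are assumptions, because the documents give none.

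- 200 patients: 100 below PSA 2 (33, 33 and 34 in three strata) and 100 at or above it (50 and 50 in two strata).
- Detection d1 in post-prostatectomy recurrence and d2 in the second type (prostate in place or known metastases), with no dependence on PSA within either type.
- Share s of the second type at PSA 2 or above, and initially none of it below.

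Detection is d1 below PSA 2 and (1 − s)·d1 + s·d2 above. With d1 = 0.50, d2 = 0.90 and s = 0.5, the upper rate is 0.5 × 0.50 + 0.5 × 0.90 = 0.70. The pooled rate is 0.60, and the noncentrality of the chi-square is [100 × 0.10² + 100 × 0.10²] / (0.60 × 0.40) = 2 / 0.24 = 8.33. On 4 degrees of freedom (critical value 9.49) that is significant about 62% of the time by the approximation and 63% by simulation. Simulated results for the planned five-stratum test at the 5% level:

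| Assumed detection | Share s | Rate below / above PSA 2 | Significant |
|---|---|---|---|
| 50% v 90% | 30% | 50% / 62% | 24% |
| 50% v 90% | 50% | 50% / 70% | 63% |
| 50% v 90% | 70% | 50% / 78% | 94% |
| 60% v 85% | 30% | 60% / 67.5% | 12% |
| 60% v 85% | 50% | 60% / 72.5% | 29% |
| 60% v 85% | 70% | 60% / 77.5% | 56% |

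The assumption that none of the second type lies below PSA 2 is the extreme case, and the inclusion criteria do not impose it. If 15% of patients below PSA 2 are of the second type, the 50% v 90% rows fall to about 9%, 34% and 77%. If the share is the same in all strata, the test is significant 5% of the time, its nominal level.

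A second simulation took post-prostatectomy patients spread evenly over the five strata at 65% detection, and post-radiation plus histology-free patients at 80% or 95%. These made up 10 to 30% and 0 to 10% of the cohort, and the routes without a floor were left out. The pooled test was significant in 6% to 70% of trials with 200 patients and 7% to 96% with 400. The same test within post-prostatectomy patients stayed at 4% to 6%.

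**The case against.** The strongest reply is that eligibility fixes much less than the table of floors suggests. Histologically proven initial staging and routes 2B to 2D have no PSA floor, and patients assessed on treatment under 2D may have a low PSA. In-place prostates and known metastases can therefore occur in any stratum, and case mix could narrow or even reverse the gradient. This stands. A reader might infer that the lower strata contain only patients without a prostate, or that the plan will necessarily produce a spurious rise with PSA. The documents support neither inference.

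Nor does post-radiation mean prostate in place. Nothing excludes patients irradiated after prostatectomy, and some of them could qualify at 0.2.

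It is also tempting to quote the size from a simple two-group test of PSA below against above 2, which gives about 40%, 82% and 98% for the 50% v 90% case. That is not the planned test and overstates the effect.

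Section 1.1.9.2 helps in part. If its split is applied to detection rate, initial-staging patients leave the subsequent-group table. They remain in the whole-cohort table, and the subsequent group still pools recurrence after prostatectomy, recurrence after radiation and routes 2B to 2D.

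Finally, detection rate is not a listed primary or secondary endpoint, and the plan attaches no hypothesis or decision rule to the comparison. A marginal association between PSA and detection is a valid description of the patients scanned. This limits the importance of the point, but does not make the pooled test informative about PSA within a recurrence type.

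**Conclusion.** The point holds in a limited form. Route-specific PSA floors mean that, among biochemical recurrences, the mix of patients differs by construction below and above 2.0 ng/mL, and the planned chi-square does nothing to separate that from PSA. A difference between strata can therefore partly reflect case mix.

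Neither direction nor size can be determined from the documents. Under the assumptions shown for 200 patients, the chance of a significant result with no PSA effect within type runs from the nominal 5% (equal mix everywhere) to 94% (50% v 90% detection, a 70% share above PSA 2 and none below). These figures show what is possible and do not forecast this trial. The issue is minor: it concerns a supporting analysis, and the primary endpoint on management change is untouched.

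**What to change.** In section 1.1.9.5:

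- Report PSA-stratified detection by entry route: 2A a in all five strata, 2A b in its two reachable strata, 2B to 2D, and initial staging.
- Base any inference about PSA on the five-stratum test within post-prostatectomy recurrence (2A a), or on a logistic model with PSA and entry route.
- Keep the pooled comparison if wanted, labelled as descriptive and not adjusted for case mix.

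The cost is SAP wording, additional table columns and fewer patients in the tested comparison. Entry route must also be captured as an analysis variable. It has to be established to confirm eligibility, but the documents do not say that it is recorded as a data item. Eligibility and study procedures do not change.
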